6.4.1.6 Period of Observation for Adverse Events

For the purposes of this study, the period of observation extends from the time the patient gives his study-specific informed consent until the end-of-study procedures are completed.

If the Investigator detects an SAE in a study patient after the end of the period of observation and considers the event possibly related to prior study treatment, he or she should contact the Sponsor to determine how the AE should be documented and reported.

6.4.1.7 Documenting, Reporting, and Eliciting Adverse Events

All AEs reported or observed during the study will be collected and recorded on the AE page of the eCRF for each patient from the date the ICF was signed until the end of their participation in the study, ie, the patient has discontinued or completed the study.

Adverse events may be volunteered spontaneously by the patient, or discovered by the study staff during physical examinations or by asking an open, non-leading question such as, “How have you been feeling since you were last asked?” All AEs and any required remedial action will be recorded. The nature of the AE, date (and time, if known) of the AE onset, date (and time, if known) of the AE outcome to date, severity, and action taken for the AE will be documented together with the Investigator’s assessment of the seriousness of the AE and causal relationship to study medication and/or study procedure.

All AEs should be recorded individually in the study patient’s own words (verbatim) unless, in the opinion of the Investigator, the AEs constitute components of a recognized condition, disease or syndrome. In the latter case, the condition, disease or syndrome should be named rather than each individual symptom. The AEs will subsequently be coded using the latest version of Medical Dictionary for Regulatory Activities (MedDRA).

6.4.1.8 Notification About Serious or Unexpected Adverse Events

The Investigator will review each SAE (Section 6.4.1.2) and evaluate the intensity and the causal relationship of the event to study medication. All SAEs will be recorded from signing of informed consent until follow-up.

The Investigator is responsible for providing notification to the Sponsor or designee of any SAE, whether deemed related to study medication or not, that a patient experiences during their participation in study within 24 hours of becoming aware of the event.

As a minimum requirement, the initial notification should provide the following information:

- Study number;
- Patient number;
- Gender;
- Date of birth;
- Name of Investigator and full study site address;
- Details of SAE;
- Criterion for classification as “serious”;
- Study medication code, or name if unblinded, and treatment start date and stop date, if applicable;
- Date of SAE onset;
- Causality assessment (if sufficient information is available to make this classification).

The Sponsor will request clarification of omitted or discrepant information from the initial notification. The Investigator or an authorized delegate is responsible for faxing the requested information to the Sponsor within 24 hours of the Sponsor’s request.

Initial reports of SAEs must be followed later with detailed descriptions, including clear photocopies of other documents as necessary (eg, hospital reports, consultant reports, autopsy reports), with the study patient’s personal identifiers removed. All relevant information obtained by the Investigator through review of these documents will be recorded and faxed to the Sponsor within 24 hours of receipt of the information. If a new SAE Report Form is faxed, then the Investigator must sign and date the form. The Sponsor may also request additional information on the SAE, which the Investigator or an authorized delegate must fax to the Sponsor within 24 hours of the request.

The SAE reporting contact information will be provided to all participating study sites by the CRO before study initiation.

6.4.1.9 Exceptions

Visits to urgent care or emergency room facilities may not warrant reporting as SAEs unless the patient is admitted to the hospital or the event meets other “serious” criteria. As discussed in Section 6.4.1.2, medical and scientific judgment should be exercised in deciding whether an AE is serious. Events that are not clearly meeting “serious” criteria can be discussed on a case-by-case basis with the Medical Monitor to help the Investigator determine whether the event meets “serious” criteria.

6.4.1.10 Follow-Up of Adverse Events

All AEs must be reported in detail on the appropriate page in the eCRF and followed to satisfactory resolution, until the Investigator deems the event to be chronic or not clinically significant, or until the patient is considered to be stable.

A follow-up telephone call will be performed for those patients with an ongoing AE which the Investigator believes to be not related to study medication administration. A follow-up visit to the study site may occur for those patients with an ongoing AE which the Investigator believes to be possibly related to study medication administration.

All AEs must be reported in detail on the appropriate page in the eCRF and followed until they are resolved or stable, or judged by the Investigator to be not clinically significant.

6.4.2 Other Safety Assessments

6.4.2.1 C-SSRS

The C-SSRS will be completed at screening, baseline, and at every subsequent scheduled clinic visit (Table 6-1). Details of the C-SSRS are presented in Section 6.1.13.

6.4.2.2 YMRS

The YMRS will be completed at screening, baseline, and at every subsequent scheduled clinic visit (Table 6-1). Details of the YMRS are presented in Section 6.1.15.

6.4.2.3 Abnormal Involuntary Movement Scale

The AIMS ([Guy, 1976](#)) measures facial and oral movements, extremity movements, and trunk movements. Seven items are rated on a scale from none (0) to severe (4). A score of “mild” (2) in 2 or more categories or a score of “moderate” or “severe” in any 1 category results in a positive AIMS score (ie, the scores are not averaged). Additionally, overall severity is scored on the basis of severity of abnormal movements and incapacitation due to abnormal movements. The patient’s awareness of and distress caused by the abnormal movements are also noted. The AIMS is to be completed at baseline and periodically throughout the study as specified in the schedule of events (Table 6-1).

6.4.2.4 Barnes Akathisia Rating Scale

The BARS is a rating scale for drug-induced akathisia developed by Barnes ([1989](#)). It includes the rating of observable restless movements, the subjective awareness of restlessness, and the distress associated with the akathisia. There is also a global rating for severity. The scale is completed by the Investigator or an expert site-based rater after a standard examination. Objective akathisia, subjective awareness and subjective distress are rated on a 4-point scale from 0 to 3, yielding a total score from 0 to 9. The global clinical assessment of akathisia is rated separately, on a 5-point scale from 0 to 4. The BARS is to be completed at baseline and periodically throughout the study as specified in the schedule of events (Table 6-1).

6.4.2.5 Simpson Angus Scale

The SAS is a measure of extrapyramidal side effects ([Simpson, 1970](#)). Ten items including rating gait, arm dropping, shoulder shaking, elbow rigidity, wrist rigidity, leg pendulousness, head rotation, glabella tap, tremor, and salivation are rated on a scale from 0 (normal) to 4 (extreme in severity). The SAS should be conducted by the Investigator or an expert site-based rater in a room where the patient can walk a sufficient distance to allow a natural pace (eg, 15 paces). Each side of the body should be examined. The SAS is to be completed at baseline and periodically throughout the study as specified in the schedule of events (Table 6-1).

6.4.2.6 Vital Sign Measurements

Vital signs will be measured at screening and at every subsequent scheduled clinic visit (Table 6-1). Details of the vital sign measurements are presented in Section 6.1.5.

6.4.2.7 ECG Assessments

The ECG assessments will be performed at screening and periodically throughout the study, as scheduled (Table 6-1). Details of the ECG assessments are presented in Section 6.1.4.

6.4.2.8 Physical and Neurological Examination

The physical and neurological examinations will be conducted at screening and periodically throughout the study, as scheduled (Table 6-1). Details of the physical and neurological examinations are presented in Section 6.1.3.

6.4.2.9 Laboratory Analyses

Blood and urine samples collected from patients will be forwarded to a central laboratory for analysis. The Investigator must review all laboratory results for all patients. If a laboratory value is reported as deleted, cancelled, unable to perform, or otherwise missing, the test must be repeated as soon as possible. If the Investigator determines that the missing value does not require an immediate repeat, he/she must provide clinical reasoning to the Sponsor or its representative.

Additional details regarding sample collections, processing and specific testing can be found in the study reference manual.

All samples for clinical laboratory analysis will be collected after an overnight fast (≥ 10 hours), after any scheduled ECG or vital signs have been recorded, and prior to dosing with study medication. Samples for clinical laboratory analysis will be used only for the evaluation of safety and tolerability.

The following clinical analytes will be determined:

Hematology: hematocrit; hemoglobin; HbA_{1c}; red blood cell count with indices (mean corpuscular volume, mean corpuscular hemoglobin, and mean corpuscular hemoglobin concentration); reticulocytes; white blood cell count and differential (neutrophils, lymphocytes, monocytes, eosinophils, and basophils) reported as percent (%) and absolute

values; and platelets (platelet count, prothrombin time and partial thromboplastin time, international normalization ratio).

Clinical chemistry: albumin; alkaline phosphatase; blood urea nitrogen; gamma-glutamyl transferase; calcium; creatinine; glucose; insulin; cholesterol (high-density lipoprotein and low-density lipoprotein [LDL] [calculated] and homogenous LDL will be reported, and homogenous LDL will be reflexed if a patient's triglycerides are >400); triglycerides; phosphate; potassium; prolactin; ALT; AST; lactate dehydrogenase; sodium; chloride; bilirubin (total, direct); total protein; uric acid; creatine phosphokinase. Thyroid panel (thyroid-stimulating hormone) will be assayed at Screening (Visit 1) and at Visit 8 (end of Treatment Period) or at Visit 9 (Early Discontinuation). If the result is abnormal, the free thyroxine and free triiodothyronine will be assayed.

[figure not shown]
Urinalysis: macroscopic (pH, specific gravity, glucose, protein, ketones, nitrates, blood) and microscopic – report only if present (red blood cells/high-power field, white blood cells/high-power field, casts, epithelial cells, crystals, granulation).

[figure not shown]
Serology: anti-HIV antibodies, hepatitis B surface antigen, and hepatitis C antibody (only during screening).

Drug Assays: Lithium and valproate blood levels will be assessed at screening and at each specified visit to assess maintenance within the respective therapeutic ranges.

6.5 Safety Monitoring Committee

No safety monitoring committee will be used for the study.

A large rectangular area of the page is completely blacked out, indicating that the original content has been redacted for confidentiality.

6.8 Pregnancy

Pregnancy is not regarded as an AE unless there is a suspicion that an investigational product may have interfered with the effectiveness of a contraceptive medication. Any pregnancy that occurs during study participation must be reported using a clinical study pregnancy form. To ensure patient safety, each pregnancy must be reported to the Sponsor within 2 weeks of learning of its occurrence. The pregnancy must be followed up to determine outcome (including spontaneous miscarriage, elective termination, normal birth, or congenital abnormality) and status of mother and child, even if the patient was discontinued from the study. Pregnancy complications and elective terminations for medical reasons should not be reported as an AE or SAE. Spontaneous miscarriages must be reported as an SAE.

Completion of the pregnancy form is not required for screen-failed patients who have had positive pregnancy test(s).

Any SAE occurring in association with a pregnancy brought to the Investigator's attention after the patient has completed the study, and considered by the Investigator as possibly related to the study treatment, must be promptly reported to the Sponsor.

7 Statistical and Analytical Plan

A formal and detailed statistical analysis plan (SAP) will be finalized prior to the planned interim analysis and will provide further details regarding the definition of analysis endpoints, analysis methodology, and the interim analysis to address all study objectives. Changes made to the data analysis methods as described in this protocol will be documented in the SAP and will not necessitate a protocol amendment. All departures from the statistical analyses described in the approved protocol, whether made before or after unblinding, will be documented, and justified in the final clinical study report.

A blinded data review will be conducted prior to unblinding the patients' treatment assignments for assessing the accuracy and completeness of the study database and defining analysis sets.

[figure not shown]

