6.4.1 Adverse Events

The Investigator is responsible for reporting all AEs that are observed or reported during the study, regardless of their relationship to study medication or their clinical significance.

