6.4.1.1 Definition of Adverse Event

An AE is any untoward medical occurrence in a study patient administered a study medication, whether or not considered drug related. This can be any unfavorable and unintended sign (such as an abnormal laboratory finding), symptom, or disease temporally associated with the use of a study medication, without any judgment of causality.

The AE may be:

- A new illness;
- A worsening sign or symptom of the condition under treatment, or of a concomitant illness;
- An effect of the study medication, including comparator; or
- A combination of 2 or more of these factors.

No causal relationship with the study medication or with the clinical study itself is implied by the use of the term AE.

Surgical procedures themselves are not AEs; they are therapeutic measures for conditions that require surgery. The condition for which the surgery is required may be an AE. Planned surgical measures, if permitted by the clinical study protocol and the conditions leading to those measures are not AEs.

All AEs fall into the categories of “nonserious” or “serious” (Sections 6.4.1.2 and 6.4.1.3).

Any abnormal laboratory test results (hematology, clinical chemistry, or urinalysis) or other safety assessments (eg, ECGs, vital sign measurements), including those that worsen from baseline, felt to be clinically significant, in the medical and scientific judgment of the investigator, are to be recorded as AEs or SAEs.

However, any clinically significant safety assessments that are associated with the underlying disease, unless judged by the investigator to be more severe than expected for the patient's condition, are not to be reported as AEs or SAEs.

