6.4.1.2 Definition of Serious Adverse Event

An SAE is defined as any untoward medical occurrence that at any dose:

- Results in death;
- Is life threatening;
- Requires hospitalization or prolongation in existing hospitalization;
- Results in persistent or significant disability or incapacity; or
- Is a congenital anomaly or birth defect.

The term "life threatening" refers to an event in which the patient is at risk of death at the time of the event; it does not refer to an event, which hypothetically might have caused death if it were more severe.

Medical and scientific judgment should be exercised in deciding whether an AE is serious. Some important medical events that may not result in death, be life threatening, or require hospitalization may be considered SAEs when they may jeopardize the patient such that medical or surgical intervention is needed to prevent 1 of the outcomes previously listed. Examples of such medical events include intensive emergency treatment for an allergic reaction, blood dyscrasias or convulsions that do not result in inpatient hospitalization, and the development of drug dependency or drug abuse.

If either the Sponsor or Investigator believes that any event is serious, the event must be considered and evaluated by the Sponsor for possible expedited reporting.

Clarification of the difference between "serious" and "severe":

The term "severe" is often used to describe the intensity (severity) of a specific event (as in mild, moderate, or severe myocardial infarction); the event itself, however, may be of relatively minor medical significance (such as a severe headache). This is not the same as

“serious,” which is based on patient/event outcome or action criteria usually associated with events that pose a threat to a patient’s life or functioning. Seriousness (not severity) serves as a guide for defining regulatory reporting obligations.

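### Protocol 6.8 keeps pregnancy complications out of AE and SAE reporting, with no exception for serious on-study complications other than miscarriage, in conflict with 6.4.1, 6.4.1.1, 6.4.1.2 and 6.4.1.8

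*Protocol*

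**What the plan says.** **The pregnancy rule.** Protocol 6.8 does not count pregnancy as an AE unless the product is suspected of having interfered with a contraceptive. Each pregnancy goes to the Sponsor on a pregnancy form within 2 weeks of the site learning of it, and is followed for its outcome and for the status of mother and child. The section then says: "Pregnancy complications and elective terminations for medical reasons should not be reported as an AE or SAE". It makes spontaneous miscarriage an SAE. Its last paragraph asks for prompt reporting of possibly related pregnancy-associated SAEs that come to light after the patient has completed the study.

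**The general rules.**
- Protocol 6.4.1: "The Investigator is responsible for reporting all AEs that are observed or reported during the study".
- Protocol 6.4.1.1: "An AE is any untoward medical occurrence in a study patient administered a study medication, whether or not considered drug related". Surgical procedures are not AEs in themselves, but "The condition for which the surgery is required may be an AE".
- Protocol 6.4.1.2 lists the criteria that make an occurrence serious. One is "Requires hospitalization or prolongation in existing hospitalization".
- Protocol 6.4.1.6: "the period of observation extends from the time the patient gives his study-specific informed consent until the end-of-study procedures are completed".
- Protocol 6.4.1.8 has all SAEs recorded from consent to follow-up. Any SAE during participation is notified within 24 hours, whether or not it is thought related.

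None of these general sections mentions pregnancy or refers to 6.8.

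**The concern.** The exclusion in 6.8 is not limited by seriousness. A complication that meets a criterion in 6.4.1.2 is an SAE under the general rules, yet 6.8 tells the site not to report it as one. Only miscarriage is exempted from that instruction on study.

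What is at stake is the routine capture and timing of individual serious cases. A site that follows 6.8 would leave the event out of the AE and SAE records and would not use the 24-hour route. This matters more here because the trial has no safety monitoring committee (6.5) and no external data monitoring committee (10.1.1). Section 10.4 also makes review of serious, unexpected and related AEs a possible ground for suspending study treatment. Reporting of single cases is thus a main safeguard.

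**Working it through.** **Text check.** The plan gives no figure to reproduce. Take a participant who becomes pregnant on study and is admitted to hospital, before her end-of-study procedures, with a complication other than miscarriage.

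| Section | Instruction for this event |
|---|---|
| 6.4.1 and 6.4.1.1 | It is an untoward medical occurrence, so an AE, and is to be reported |
| 6.4.1.2 | It required admission, so it is an SAE |
| 6.4.1.8 | Record it as an SAE and notify within 24 hours, related or not |
| 6.8 | Do not report it as an AE or SAE |

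The last row cannot be followed together with the others.

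**Do the other routes cover the case?**
- The 2-week limit in 6.8 runs from learning of the pregnancy, not of the complication. The section sets no deadline for an on-study complication.
- Outcome follow-up continues even after discontinuation, but it is not SAE reporting.
- Section 6.4.1.2 also says: "If either the Sponsor or Investigator believes that any event is serious, the event must be considered and evaluated by the Sponsor". That helps only if someone raises an event that 6.8 says not to report as an SAE.
- For a possibly related SAE found after the observation period, 6.4.1.6 says of the Investigator that "he or she should contact the Sponsor to determine how the AE should be documented and reported". This does not reach events inside the period.

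**Scope.** The conflict exists only within the observation period. Pregnancy is itself a listed reason for withdrawal (4.2.1), which can shorten that period. For a medically indicated termination, only the underlying condition is at issue, because 6.4.1.1 takes procedures out of the AE definition.

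**How often could it arise?** Inputs:
- N = 520 (4.1), or 600 if all three arms reach the cap of 200 in 7.5.9.
- Contraceptive failure of 1% per year, the limit in inclusion criterion 5, which assumes consistent and correct use.
- 56 days, from Day 1 to the last follow-up visit (4.2).
- Share of patients of childbearing potential: not in the documents; assumed to be 25%, 50% or 100%.

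Expected pregnancies = N × share × 0.01 × 56 / 365.25.

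| Share | N = 520 | N = 600 |
|---|---|---|
| 100% | 0.80 | 0.92 |
| 50% | 0.40 | 0.46 |
| 25% | 0.20 | 0.23 |

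For example, 520 × 1.00 × 0.01 × 56 / 365.25 = 0.797. Serious complications other than miscarriage inside the window would be some fraction of these counts. The documents give no basis for that fraction, so none is applied.

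**The case against.** The strongest defence is that 6.8 is a deliberate specific rule that narrows the general ones. Naming miscarriage as the event that stays an SAE is how such a rule with an exception is often written. Nor does the silence of 6.4.1.9 on pregnancy prove much. That section deals with urgent-care and emergency visits and borderline seriousness, and 6.4.1.1 holds a carve-out of its own for findings tied to the underlying disease. This stands as far as it goes: the documents do not rule out a deliberate carve-out. But it does not remove the problem, because under that reading a serious on-study complication still stays out of the SAE record and the 24-hour route.

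Stronger conclusions that a reader might draw are not supported:
- **That 6.8 makes a possibly related serious complication reportable after completion but not on study.** The exclusion sentence has no time limit, so it may apply after completion too. Alternatively, the last paragraph may simply add a post-completion duty to 6.4.1.8. The text does not force the asymmetry.
- **That 6.8 cannot be read as a separate route for pregnancy events.** It can, as above.
- **That the pregnancy counts are ceilings.** The 1% rate presumes consistent and correct use, and the count starts at Day 1 whereas the observation period starts at consent.
- **That the Sponsor would certainly never review such an event.** The backstops in 6.4.1.2 and 6.8 could still bring it to the Sponsor.

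It is also fair to say that the event is rare and that the wording may have been superseded. The SAP introduction rests on protocol version 1.6 of 23 March 2020, which was not supplied.

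**Conclusion.** The point holds for the supplied 2019 wording. For an on-study pregnancy complication other than miscarriage that meets the SAE criteria, 6.8 and the general safety sections give instructions that cannot all be followed, and following 6.8 gives the wrong reporting result even if the rule was intended.

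The practical size is small: fewer than one expected pregnancy in the trial under the illustrative inputs, and fewer affected events still. This rests on the assumed childbearing-potential share and on the 1% rate holding in practice. Endpoints, power and study-level rates are not affected. The case for correction is the proper handling of individual serious events. Whether action is still needed depends on version 1.6.

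**What to change.** First check whether protocol version 1.6 already resolves the conflict. If it does not, add one sentence to 6.8: an on-study pregnancy complication, or the condition that leads to a medically indicated termination, is reported as an SAE on the 6.4.1.8 timeline if it meets the 6.4.1.2 definition, in addition to the pregnancy form. Put a matching line in the sites' safety reporting instructions.

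The drafting cost is trivial. The procedural cost is an amendment that needs IRB/IEC approval (10.2.1) across approximately 93 sites (4.1), so it is best bundled with another amendment. Sample size, endpoints and analyses do not change.
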